5.3.1.4 Primary analysis of PSP-QoL

The PSP-QoL is a participant-reported outcome measure developed specifically for assessing the health-related quality of life in people living with PSP. It is a validated 45-item questionnaire and visual analog scale that is comprised of two subscales: physical health state (22 items), which covers mobility, dysarthria, dysphagia, visual disturbances, self-care, and activities of daily living, and mental health state (23 items), which covers emotional, cognitive and social functioning. Items are given a 6-reponse option format (No Problem, Slight Problem, Moderate Problem, Marked Problem, Extreme Problem and Not Applicable). The subscale results are calculated from summing the respective items for that subscale and transforming the scores into a range of 0 to 100, with higher scores indicating a greater impact of the disease on the aspect measured. The transformation algorithm for physical and mental scales is $100 * (\text{observed score} - \text{minimal possible score}) / (\text{max possible score} - \text{minimal possible score})$ where the minimal possible score is 0.

The PSP-QoL also comprises of a Life Satisfaction rating gauge, which is a visual analog scale with a range of 0 (worst) to 100 (best).

The primary analysis of change from baseline PSP-QoL physical scale, mental scale and life satisfaction rating scale scores will be based on the base MMRM model described in Section 5.1. A line plot of adjusted mean change from baseline over time will be provided.

5.3.1.5 Sensitivity and Supplementary analysis

The following sensitivity and supplementary analyses that are planned for the primary efficacy endpoint will also be conducted for the key secondary efficacy endpoints:

- Pattern mixture model
- Censoring after intercurrent events
- Per-protocol analysis
- Slope analysis
- Divergence effect analysis

For the 3 domain z-scores of the PSP cognitive composite battery, the baseline value and the change from baseline at each post-baseline visit will be summarized by treatment group. The same

MMRM model as the primary analysis will also be applied to the domain z-scores. A forest plot of adjusted mean change from baseline versus placebo at Week 52 from each domain will be provided.

For the total score of the 11 RBANS tests, the baseline value and the change from baseline at each post-baseline visit will be summarized by treatment group. The same MMRM model as the primary analysis will also be applied to this total score of 11 RBANS tests.

For CGI-C, the categorical summary of the proportions (1) in each score category (1-7) and (2) improvement, no change and worsening will be performed.

5.3.2 Non-Key Secondary Efficacy Endpoints

Non-key secondary endpoints are tested at an uncontrolled alpha level of 0.05 per endpoint. The P values resulting from these analyses are considered as nominal and descriptive in nature.

Sections 5.3.2.1 through 5.3.2.6 provide additional details about the efficacy assessments.

5.3.2.1 SEADL Scale

The SEADL scale is a means of assessing a person's ability to perform daily activities in terms of speed and independence through a percentage figure. The rating is determined by a qualified staff member according to the participant's self-reported functional ability of specific criteria, with 100% indicating total independence (healthy), falling to 0% (bedridden), which indicates a state of complete dependence. The SEADL comprises of one question to be rated by selecting a value ranging from 100% to 0%, in 11 answer options: 100%, 90%, 80%, 70%, 60%, 50%, 40%, 30%, 20%, 10%, and 0%. Each answer option has specific clinical descriptors and only one answer can be chosen.

The primary analysis of change from baseline SEADL will be based on the base MMRM model described in Section 5.1.

Categorical summary of the proportions in each score category (0%-100%) will also be performed.

5.3.2.2 CGI-S

The CGI-S measures the overall global clinical impression of disease severity using a 7-point scale. The CGI-S asks the clinician one question: "Considering your total clinical experience with this particular population, how mentally ill is the subject at this time?" which is rated on the following 7-point scale: 1 for "Normal, not at all ill"; 2 for "Borderline mentally ill; 3 for "Mildly ill; 4 for "Moderately ill; 5 for "Markedly ill; 6 for "Severely ill; 7 for "Among the most extremely ill subjects". Only one answer can be chosen.

The primary analysis of change from baseline CGI-S scores will be based on the base MMRM model described in Section 5.1.

Categorical summary of the proportions in each score category (1-7) will also be performed.

5.3.2.3 Phonemic Fluency Test

Phonemic fluency is a sensitive test for assessing frontal lobe dysfunction. Participants are given a letter of the alphabet and asked to name as many words as they can that start with that letter in 1 minute.

The score for each trial is auto-calculated as follows:

- Trial 1: Total number of correct responses for the first letter (range 1 to 40);
- Trial 2: Total number of correct responses for the second letter (range 1 to 40).

The total score from the two trials will be used for analysis.

The visit assignment for each form with associated letters is shown below.

| Form | Letters | Visits |
|------|---------|--------------------|
| A | F, L | Screening, Week 24 |
| B | T, S | Visit 1, Week 48 |
| C | R, M | Week 12, Week 36 |

The primary analysis of change from baseline phonemic fluency test scores will be based on the base MMRM model described in Section 5.1.

5.3.2.4 WAIS-IV Letter Number Sequencing Task

The WAIS-IV (Wechsler Adult Intelligence Scale--IV) LNS Task contains 10 items. Each item has 3 trials, and all 3 trials need to be rated as Incorrect (0) or Correct (1) before the rater is allowed to move to the following item.

The LNS total raw score (0 to 30 range) is auto-calculated by summing the 10 individual item scores (range 0 to 3 for each item).

The longest LNS total raw score (2 to 8 range) is auto-calculated from the count of the longest sequence (string) of numbers and letters correctly reproduced by participant.

The primary analysis of change from baseline LNS total raw scores and change from baseline longest LNS total raw score will be based on the base MMRM model described in Section 5.1.

5.3.2.5 Color Trails Test

The CTT is a language-free version of the Trail Making Test and was developed to allow for broader cross-cultural assessment. The form consists of two parts, CTT 1 and CTT 2.

For CTT 1, the participant simply has to connect the numbered circles, in order, from 1 to 25, by drawing a continuous line from circle to circle.

For CTT 2, the test demand is the same, except the participant must alternate between colors while connecting the circles.

The score for each part of the test is the total time required for completion in seconds. The maximum time allowed for each test trial is 240 seconds.

The primary analysis of change from baseline CTT 1 will be based on the base MMRM model described in Section 5.1.

The primary analysis of change from baseline CTT 2 will be based on the base MMRM model described in Section 5.1 along with removing the CTT 2 factor in the model.

5.3.2.6 **MoCA**

The MoCA is a one-page 30-point test designed as a rapid screening instrument for mild cognitive dysfunction. Scores for 8 cognitive domains are calculated: visuospatial/executive (maximum of 5 points); naming (maximum of 3 points); memory (total number of words remembered correctly across 2 trials; no points); attention (sum of scores for 3 questions; maximum of 6 points); language (sum of scores for 2 questions; maximum of 3 points); abstraction (maximum of 2 points); delayed recall (maximum of 5 points); orientation (maximum of 6 points). The total score is calculated by summing all domain scores (excluding memory) and adding a point for participant's education level ≤ 12 years. The maximum total score is 30 points; a score of 26 or above is considered normal.

The primary analysis of change from baseline MoCA total scores will be based on the base MMRM model described in Section 5.1.

5.3.2.7 **RBANS**

The RBANS was developed for the dual purposes of identifying and characterizing abnormal cognitive decline in the older adult. The full battery is composed of 12 subtests: List Learning; Story Memory; Figure Copy; Line Orientation; Picture Naming; Semantic Fluency; Digit Span; Coding; List Recall; List Recognition; Story Recall; and Figure Recall. Five Sum of Index Scores are calculated from the 12 subtests:

- List Learning and Story Memory
- Figure Copy and Line Orientation
- Picture Naming and Semantic Fluency
- Digit Span and Coding
- List Recall, List Recognition, Story Recall and Figure Recall

The total scale score is calculated from the 5 Index Scores which will be used for the primary analysis of RBANS. The primary analysis of change from baseline RBANS scores will be based on the base MMRM model described in Section 5.1. A line plot of adjusted mean change from baseline over time will be provided. A listing will also be generated.

For the 5 RBANS index scores, the baseline value and the change from baseline at each post-baseline visit will be summarized by treatment group. The same MMRM model as the primary analysis will also be applied to the 5 sum of index scores.

5.3.2.8 Volumetric MRI Analysis

Brain volumetric measurements will be carried out to estimate brain volumes of 7 primary brain regions of particular relevance in PSP: ventricles, whole brain, midbrain, pons, superior cerebellar peduncle, third ventricle and frontal lobes. In addition, volumes of secondary brain structures (e.g., brainstem, cerebral cortex, cerebrum, lateral ventricles, left caudate nucleus, right caudate nucleus, medulla oblongata, total gray matter and total white matter) and other brain structures (e.g. cerebellum, fourth ventricles, left/right hippocampus, left/right inferior ventricles, left/right occipital lobe, left/right parietal lobe, left/right temporal lobe) will be measured.

The change from baseline in absolute volumes which pass endpoint QC and are measured on the same MRI scanner as used at screening will be the primary MRI efficacy endpoint for analysis. The efficacy MRI analysis population will be used for the analysis of volumetric MRI data. The absolute values, change and percent change from baseline in volumes of all brain regions will be summarized by treatment group and by visit. The change from baseline in volumes of the primary regions and the secondary regions will be analyzed using the MMRM model described in Section 5.1. For the primary brain regions, the adjusted mean change from baseline in volumes will be presented graphically by line plot. A forest plot for adjusted mean % change from baseline at Week 52 for the primary brain regions will also be provided. A listing of the primary brain region volumetric MRI data will be provided.

5.4 Tertiary Efficacy Endpoints

[REDACTED]

[REDACTED]

- [REDACTED]
- [REDACTED]

[REDACTED]

[REDACTED]

[REDACTED]

[REDACTED]

[REDACTED]

[REDACTED]

[REDACTED]

[REDACTED]

[REDACTED]

[REDACTED]

[REDACTED]

[REDACTED]

[REDACTED]

[REDACTED]

[Redacted]

[Redacted]

[Redacted]

- [Redacted]
- [Redacted]
- [Redacted]
- [Redacted]
- [Redacted]
- [Redacted]
- [Redacted]
- [Redacted]

[Redacted]

- [Redacted]
- [Redacted]

[Redacted]

- [Redacted]
- [Redacted]
- [Redacted]
- [Redacted]

[Redacted]

[Redacted]

- [Redacted]
- [Redacted]
- [Redacted]
- [Redacted]
- [Redacted]

| | | |
|------------|------------|------------|
| [REDACTED] | [REDACTED] | |
| [REDACTED] | [REDACTED] | [REDACTED] |
| [REDACTED] | [REDACTED] | [REDACTED] |
| [REDACTED] | [REDACTED] | [REDACTED] |

[REDACTED]

[REDACTED]

[REDACTED]

[REDACTED]

[REDACTED]

[REDACTED]

[REDACTED]

[REDACTED]

- [REDACTED]
- [REDACTED]
- [REDACTED]
- [REDACTED]

[REDACTED]

[REDACTED]

[REDACTED]

[REDACTED]

[REDACTED]

[REDACTED]

- [REDACTED]
- [REDACTED]
- [REDACTED]
- [REDACTED]

[REDACTED]

[REDACTED]

[REDACTED]

[REDACTED]

5.5 Subgroup Analysis

Subgroup analyses will be performed for the primary and the key secondary endpoints. The following pre-defined subgroups will be considered:

Demographics:

- Sex (female, male)
- Age (\leq median, $>$ median);
- Race (White, Non-White);
- Region (US, Non-US);

Baseline characteristics:

- Baseline color trails 2 test categorization (≤ 170 or > 170 seconds);
- Time since first onset of PSP symptom (\leq median, $>$ median)
- Baseline 28-item PSPRS total score (\leq median, $>$ median)
- Baseline 15-item PSPRS total score (\leq median, $>$ median)
- Baseline use of Parkinson's disease medication (yes, no; see Section 4.4 for definition of Parkinson's Disease medication use at baseline);
- Possible or probable PSP
- 28-item PSPRS Gait item 26 at baseline (<3 , ≥ 3)
- tau haplotype (H1/H1, H1/H2, or H2/H2)

Subjects in each subgroup category will be analyzed separately using the same MMRM analysis of the primary and key secondary endpoints. Forest plots of adjusted mean change from baseline versus placebo at Week 52 from all subgroup analyses will also be provided. Subgroup analyses will not be performed if one of the subgroups is below 10% of the total number of subjects analyzed. Subgroup analyses will not be performed if the analysis model cannot converge.

[REDACTED]

[REDACTED]

[REDACTED]

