17. STATISTICAL CONSIDERATIONS

17.1. Sample Size Determination

Approximately 459 participants will be randomly assigned in a 2:1 ratio to receive BIIB092 or placebo (306 participants in the BIIB092 treatment group and 153 in the placebo group). Anticipating a dropout rate of approximately 25% (based on previous clinical studies in participants with PSP), approximately 345 participants (230 participants in the BIIB092 treatment group and 115 participants in the placebo group) are expected to complete the study through Week 52.

Using a two-sided, two-sample t-test with an alpha level set at 0.05, this sample size will provide 80% power to detect a difference of 3.2 points in the change in PSPRS total score from baseline to Week 52 for BIIB092 relative to placebo, assuming a common standard deviation of 9.95 [Stamelou 2016] in the change in PSPRS total score from baseline to Week 52.

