3 GENERAL CONSIDERATIONS

3.1 General Methods

This statistical analysis plan (SAP) only covers the analyses for the double-blind placebo-controlled portion of the study. Hereafter, the double-blind, placebo-controlled portion of the study will be referred to as “the study” in the rest of this SAP (e.g., completion of the study means completion of the placebo-controlled portion). A separate SAP will be prepared for the analyses of the open label extension (OLE) period and integrated analyses across both portions of the study. The analyses of selected exploratory endpoints may be documented separately. The term “subject” used in this SAP and in the analyses is equivalent to the term “participant” used in the Protocol.

Summary tables will be presented using descriptive summary statistics. For continuous variables, summary statistics will generally include: number of subjects with data, mean, standard deviation, median, 25% percentile, 75% percentile, minimum and maximum. For categorical variables, this

will generally include: number of subjects randomized or dosed, number with data, and the percent of those with data in each category.

In general, listings will include all data in the placebo-controlled and OLE periods (all data in the study), with an indicator of the study period (screening, placebo-controlled, or OLE) for each record to indicate when the event occurred.

Unless otherwise specified, baseline value is defined as the most recent non-missing measurement collected prior to the first dose. Change from baseline will be defined as post-baseline value minus baseline value.

Unless stated otherwise, all statistical tests will be 2-sided with statistical significance level of 0.05.

The statistical software SAS® will be used for all summaries and analyses.

The health care region used in the analysis (referred as region in this SAP) is defined as:

- US: United States
- Non-US: Australia, Austria, Canada, France, Germany, Greece, Italy, Russian, Spain, United Kingdom, Japan and Korea

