5.1.4 Considerations for base MMRM model for change from baseline analyses

The observed value and change from baseline for a parameter of interest will be summarized by treatment group at each post-baseline visit. A mixed model repeated measures (MMRM) model will be used as the primary analysis to analyze change from baseline using fixed effects of treatment group, time (categorical), treatment group-by-time interaction, baseline for the parameter of interest, (baseline for the parameter of interest) by time interaction, baseline Color Trails 2 test (≤ 170 or > 170 seconds) and region (see healthcare region definitions in Section 3.1). An unstructured covariance matrix will be used to model the within-subject variance-covariance errors. If the unstructured covariance structure matrix results in a lack of convergence, the heterogeneous Toeplitz covariance structure followed by the heterogeneous first-order autoregressive covariance structure will be used. The Kenward-Roger approximation will be used to estimate the denominator degrees of freedom. If the unstructured variance-covariance structure does not converge in the MMRM model and a structured model is used, the sandwich estimator will be used to get the variance of the treatment effect estimator. The adjusted mean of each treatment group, as well as the treatment group differences will be displayed with 95% CI and p-value. In the primary analysis of each endpoint, missing data are assumed to be missing at random [Rubin 1976].

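### The subgroup plan fits each category separately with its own p-value and, in the readable text, never estimates or tests whether the treatment effect differs between categories

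*SAP*

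**What the plan says.** Section 5.5 of the placebo-controlled SAP lists 12 factors for the primary and key secondary endpoints: sex, age, race, region, Color Trails 2 category, time since symptom onset, baseline 28-item PSPRS, baseline 15-item PSPRS, Parkinson's medication, possible or probable PSP, gait item 26, and tau haplotype. Four of these (age, time since onset and the two PSPRS scores) are split at the median. The method is: "Subjects in each subgroup category will be analyzed separately using the same MMRM analysis of the primary and key secondary endpoints". Forest plots of the Week 52 differences are planned, and a factor is skipped if one of its categories holds fewer than 10% of the subjects analysed.

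The model being repeated is the base MMRM of Section 5.1.4. Its only treatment interaction is with time, and its output rule is: "The adjusted mean of each treatment group, as well as the treatment group differences will be displayed with 95% CI and p-value". Section 3.1 sets the default that "all statistical tests will be 2-sided with statistical significance level of 0.05", and Section 5.1.3 exempts subgroup analyses from multiplicity adjustment.

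No treatment-by-subgroup term, contrast or heterogeneity test appears in the readable text of the protocol, the placebo-controlled SAP or the open-label extension SAP. Redacted blocks follow the subgroup text in Section 5.5, so a test hidden there cannot be excluded.

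**The concern.** The usual reason to split a trial by sex, severity or haplotype is to see whether the effect is the same across categories. The p-values planned here answer another question: whether the effect is zero within this category, in a sample that may be a tenth of the trial. A forest plot shows the two estimates side by side but gives no interval for the difference between them.

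Without that contrast, readers tend to compare significance: present in one category, absent in the other. Two categories with the same true effect can produce that pattern by chance. A smaller category may then be read as not benefiting, or a larger one as the population in which the drug works.

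**Working it through.** **Inputs.** Protocol 17.1 gives the test ("Using a two-sided, two-sample t-test with an alpha level set at 0.05"), the power ("this sample size will provide 80% power to detect a difference of 3.2 points in the change in PSPRS total score"), the spread ("assuming a common standard deviation of 9.95"), and 230 and 115 expected completers. The split within each factor is not stated. Equal halves follow from the four median splits; 75/25 and 90/10 are assumptions showing the range that the 10% floor permits.

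**Reproduce the design.** SE = 9.95 × √(1/230 + 1/115) = 1.136. Power = Φ(3.2/1.136 − 1.96) = Φ(0.856) = 80.4%; the exact noncentral t gives 80.2%. The protocol's 80% is reproduced.

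**Discordance when the true effect is 3.2 in everyone.** A category holding share f of the completers, with 2:1 allocation preserved, has SE = 1.136/√f and power p = Φ(3.2/SE − 1.96). Two categories hold different patients, so P(exactly one significant) = p₁(1 − p₂) + p₂(1 − p₁).

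| Split | SE in each | Power in each | Exactly one significant |
|---|---|---|---|
| 50/50 | 1.607, 1.607 | 51.2%, 51.2% | 2 × 0.512 × 0.488 = 50% |
| 75/25 | 1.312, 2.273 | 68.4%, 29.0% | 0.684 × 0.710 + 0.290 × 0.316 = 58% |
| 90/10 | 1.198, 3.594 | 76.2%, 14.2% | 0.762 × 0.858 + 0.142 × 0.238 = 69% |

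For equal halves, both are significant 26% of the time (0.512²) and neither 24% (0.488²).

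**Dependence on the effect, equal halves.** With both tails counted:

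| Common true effect (points) | Power per half | Exactly one significant |
|---|---|---|
| 0 | 5.0% | 9.5% |
| 1 | 9.5% | 17% |
| 2 | 23.8% | 36% |
| 2.5 | 34.3% | 45% |
| 3.2 | 51.2% | 50% |
| 3.5 | 58.6% | 49% |
| 5 | 87.5% | 22% |
| 6 | 96.2% | 7% |

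The rationale for protocol Version 5 describes 2.5 to 3.5 points as clinically meaningful; across that range the figure is 45% to 50%.

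**Dependence on information.** If all 459 randomised subjects contributed in full, SE = 9.95 × √(1/306 + 1/153) = 0.985. Power per half at 3.2 points would be 63.2%, and discordance 2 × 0.632 × 0.368 = 47%.

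**What an interaction contrast would do.** For equal halves, the SE of the difference between the two effects is √2 × 1.607 = 2.27.

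- With identical effects the contrast rejects 5% of the time. Simulation with 1,000,000 draws gave 5.0% at each split checked.
- Power is Φ(3.2/2.27 − 1.96) = 29% for effects that differ by 3.2 points.
- Power is Φ(6.4/2.27 − 1.96) = 80% for effects that differ by 6.4 points.

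**The case against.** The strongest defence is that the SAP never proposes to compare significance across subgroups. It plans forest plots, declares the analyses unadjusted and attaches no decision to them. Any harm needs a reader to make the faulty comparison. That stands, and it limits the point to interpretation. It does not remove it: the plan supplies the p-values that invite the comparison and omits the quantity that would replace it.

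A second objection is that interaction tests are no cure. With 12 factors and eight endpoints (two PSPRS totals, MDS-UPDRS Part II, CGI-C, the cognitive composite and three PSP-QoL scales) there would be 12 × 8 = 96 of them. About 0.05 × 96 ≈ 5 would be nominally significant by chance if no effect differed, and power is low. That also stands, and is why the estimate and its interval matter more than the p-value.

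Three stronger readings are tempting, but the documents do not support them:

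- **Region.** A reader might infer that the US/non-US subgroup is especially dangerous because the US and Europe/Japan have different primary endpoints. Sections 5.2 to 5.2.3 make those a matter of regulatory evidence; both endpoints are analysed in the whole ITT population. The subgroup factor is patient location, and non-US includes countries such as Australia, Canada and Korea.
- **Convergence.** The sentence "Subgroup analyses will not be performed if the analysis model cannot converge" might suggest that small subgroups are lost as soon as the unstructured covariance fails. The same MMRM carries the fallbacks of Section 5.1.4: heterogeneous Toeplitz, then heterogeneous first-order autoregressive, with a sandwich variance.
- **Near certainty across the whole plan.** With 12 factors, a reader might infer that some discordant pair is almost guaranteed. That depends on how the factors overlap, which the documents do not give; the two baseline PSPRS splits are plainly related.

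**Conclusion.** The point holds, as a matter of exploratory interpretation. On the readable text, the plan yields separate tests of zero effect in each category and no estimate or test of the difference between categories.

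At the design effect of 3.2 points on the 28-item PSPRS, identical effects in two equal subgroups give one significant and one non-significant result 50% of the time, and more often when the split is uneven. It would be wrong to state this as half the time without its conditions: it is 9.5% with no effect and 7% at 6 points.

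The calculation treats the MMRM as a completer t-test, so covariate adjustment and partial follow-up would raise subgroup power somewhat. It covers only the 28-item score, because no SD is readable for the 15-item score or the key secondary endpoints. The primary type I error is unaffected. The absence of a contrast is established only for unredacted text.

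**What to change.** In Section 5.5 of the placebo-controlled SAP, add one MMRM per factor on the full ITT population. It should contain the base-model terms plus treatment-by-subgroup and treatment-by-subgroup-by-visit. Add subgroup and subgroup-by-visit terms where the base model lacks them; Color Trails 2 category and region are already main effects.

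Beside the forest plots, report the Week 52 difference in treatment effect between subgroups with a 95% CI and a nominal interaction p-value, labelled exploratory and unadjusted. For the three-level tau haplotype, use a 2-df test with pairwise differences.

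The separate fits may stay as estimates with CIs. State that heterogeneity will be judged from the interaction contrast and not by comparing within-subgroup p-values.

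The cost is SAP wording and one further model per factor and endpoint, with no new data and no change to the primary analysis. The joint model assumes a covariance common to the subgroups. About 5% of the interaction tests will be nominally significant by chance when effects are equal, and power is limited as shown above; displaying the interval makes that limit visible.
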